#### 6.1.2 Secondary efficacy variable

To evaluate additional analgesic effect of CT001 in pediatric participants with moderate to severe pain in an acute care setting

- Maximum change from baseline in pain intensity within 30 min post IMP administration.
- Number and proportion of participants that achieve a 30% reduction in pain intensity relative to baseline within 30 min post IMP.
- Change from baseline in pain intensity at 10, 15, 20, 30, 45 and 60 min post IMP.
- Derived variables such as area under curve (AUC), peak change in pain intensity from baseline, and duration of effect will be calculated from the recorded pain assessments.

To evaluate the need for supplemental analgesic medication during the study period

- Number and proportion of children receiving additional analgesics, as assessed by timepoint.

### 6.2 Assessment of safety and tolerability

#### 6.2.1 Primary safety and tolerability variables

To investigate the safety and tolerability of IN CT001 in pediatric participants in the acute care setting experiencing pain of moderate or severe intensity.

- Sedation as assessed by sedation score on the University of Michigan Sedation Scale (UMSS) (Malviya et al, Anesthesiology 2004) at the following timepoints: baseline and 10, 15, 20, 30, 45 and 60 min after first IMP administration. If a second IMP dose is needed, sedation will be performed at the timepoints relative to first IMP administration.
- Respiratory depression, assessed by respiratory rate.
- Peripheral Oxygen saturation, as assessed by peripheral oximetry.
- Cardiovascular stability, as assessed by pulse rate.
- Number of reported Adverse Events, graded by intensity and severity.
- Number of AEs reported per participant.
- Local nasal irritation as assessed by combined participant and investigator feedback at 30 and 60 min post IMP administration.

### 6.2.2 Secondary safety and tolerability variables

To evaluate the feasibility/treatment satisfaction of the nasally administered CT001 for acute pain relief in pediatric participants in the emergency setting.

- Treatment satisfaction as assessed by responses to the question: *“How satisfied are you with the study drug that you/your child received? Please think about how it helped their pain, how it was given, any side effects, and how quickly you/your child recovered”*. Respondents will answer using a 5-point Likert scale (very unsatisfied, unsatisfied, neutral, satisfied, very satisfied).
- Feasibility (i.e. acceptance of nasal administration) will be addressed by the healthcare staff asking the child: *If you were in this situation again and needed pain medication, would you like to receive the nasal spray (relative to an injection, tablet or suppository for the pain)?* If not possible by the child, the parent/legal guardian will assess nasal acceptability. Answers will be “yes”, “no”, “I don’t know”.
- Medication errors, defined as any deviation in the IMP administration instructions that result in higher or lower dose than planned. Examples may include erroneous priming of the pump, too few/many pumps administered, etc.

## 6.3 Adverse Events and Serious Adverse Events

The Investigator should ensure thorough collection of all adverse events (AEs) and concomitant medication information associated with each participant. The Investigator should ask the participant to report any feeling of being unwell or different from usual in any way during the clinic visit to ensure that adverse event (AE) information is recorded in the participant's source notes and is then subsequently entered into the eCRF. Adverse events can be events or symptoms reported by the participant. They can also be symptoms and signs observed by study staff.

All relevant responses from the participant will be recorded in the source notes and eCRF on an AE form and graded on severity (mild, moderate, severe), seriousness and relationship to IMP (unlikely, possibly, probably). Whenever possible a diagnosis should be given and not just a list of signs and symptoms. For further details regarding the classification of AE, please see below.

All AEs are to be reviewed by the Investigator while ongoing, and subsequently documented at the point of resolution. All AEs classified as serious are to be immediately brought to the attention of the Investigator by site staff for review and action. All ongoing AEs will be followed up by the Investigator until participant discharge or resolution (i.e. AE's can thus be followed longer than 60 min post IMP is deemed needed). Additional clinic visits may be scheduled by the Investigator to follow-up on AEs according to their clinical judgement.

### 6.3.1 Baseline symptoms

A baseline symptom is defined as an event that occurs between signing of the assent / ICF until the first administration of IMP (i.e. an event that occurs during the screening period). Such events are not classified as AEs and will be recorded as baseline symptoms in the Medical History Log in the eCRF.

### 6.3.2 Definitions of Adverse Events

#### **Adverse Event (AE):**

An AE is any untoward medical occurrence in a clinical study participant administered a pharmaceutical product and which does not necessarily have a causal relationship with this treatment. An AE can therefore be any unfavourable and unintended sign (including clinically significant abnormal values from relevant tests, such as clinical safety laboratory tests, ECGs, vital signs), symptom, or disease temporally associated with the use of an IMP, regardless of whether it is considered related to the IMP.

A baseline symptom is any medical event in a clinical study subject that occurs after he/she signed the ICF up until the first administration of IMP.

A treatment emergent AE (TEAE) is any AE not present, prior to the initiation of IMP administration or any event already present that worsens in either intensity or frequency following exposure to the IMP.

Only TEAEs are collected in this study (i.e., events occurring between screening and the first IMP administration are regarded as baseline symptoms and should not be recorded in the AE log in the eCRF).

#### **Serious Adverse Events (SAEs):**

An SAE is any AE that:

- results in death

- is life-threatening (this refers to an event in which the subject was at risk of death at the time of the event; it does not refer to an event that hypothetically might have caused death had it been more severe)
- requires inpatient hospitalization or prolongation of existing hospitalization
- results in persistent or significant disability/incapacity
- is medically important (this refers to an event that may not be immediately life-threatening or result in death or hospitalization, but may jeopardize the subject or may require intervention to prevent any of the SAEs defined above)

Examples of medically important events are intensive treatment in an emergency room for allergic bronchospasm or blood dyscrasias, convulsions that do not result in hospitalization, development of drug dependency, and drug abuse.

Medical and scientific judgement should be exercised in deciding whether expedited reporting is appropriate in other situations, such as important medical events that may not be immediately life-threatening or result in death or hospitalisation but may jeopardise the subject or may require intervention to prevent one of the other outcomes listed in the definition above. These should also usually be considered serious.

#### ***Non-serious adverse event:***

Is any adverse event that does not meet the definition of an SAE.

If there is any doubt as to whether an adverse event meets the definition of an SAE, a conservative viewpoint must be taken, and the adverse event must be reported as an SAE.

#### ***Adverse Reaction:***

All noxious and unintended responses to a medicinal product related to any dose should be considered adverse drug reactions. The phrase "responses to a medicinal product" means that a causal relationship between a medicinal product and an AE is at least a reasonable possibility, i.e., the relationship cannot be ruled out. For marketed medicinal products, an adverse reaction is a response to a drug which is noxious and unintended and which occurs at doses normally used in man for prophylaxis, diagnosis, or therapy of disease or for modification of physiological function.

#### ***Unexpected Adverse Reaction:***

An adverse reaction, the nature or severity of which is not consistent with the applicable product information for the test product (Investigator's Brochure).

#### ***Suspected Unexpected Serious Adverse Reaction (SUSAR):***

Any serious adverse reaction that might be related to the study medication and are unexpected according to the definition above.

Confidential

/ v 3.2/ 18-SEP-2024

**Overdose:**

Is a dose administered to a participant that exceeds the dose prescribed to that participant. Any overdose (and associated symptoms) must, at a minimum, be recorded as a non-serious adverse event.

**6.3.2.1 Severity**

Note that severity is a description of the intensity of the AE and is not to be confused with seriousness for which the definitions in 6.3.2 apply. Both seriousness and severity of an AE need to be assessed independently.

**Mild:**

The adverse event is transient and easily tolerated.

**Moderate:**

The adverse event causes the subject discomfort and interrupts the subject's usual activities.

**Severe:**

The adverse event causes considerable interference with the subject's usual activities and may be incapacitating or life-threatening.

**6.3.2.2 Relationship to IMP**

The causal relationship between the IMP and the AE should be indicated, using a modified WHO-UMC causality categories, see Table 3.

*Table 3. WHO-UMC Causality Categories*

Causality term	Assessment criteria*
Certain	
 
• Event or laboratory test abnormality, with plausible time relationship to drug intake
 
• Cannot be explained by disease or other drugs
 
• Response to withdrawal plausible (pharmacologically, pathologically)
 
• Event definitive pharmacologically or phenomenologically (i.e. an objective and specific medical disorder or a recognized pharmacological phenomenon)
 
• Rechallenge satisfactory, if necessary
 

Probable / Likely	
 
• Event or laboratory test abnormality, with reasonable time relationship to drug intake
 
• Unlikely to be attributed to disease or other drugs
 
• Response to withdrawal clinically reasonable
 
• Rechallenge not required
 

Possible	
 
• Event or laboratory test abnormality, with reasonable time relationship to drug intake
 
• Could also be explained by disease or other drugs
 

	
 
Information on drug withdrawal may be lacking or unclear
 

Unlikely	
 
Event or laboratory test abnormality, with a time to drug intake that makes a relationship improbable (but not impossible)
 
Disease or other drugs provide plausible explanations
 

For data analysis and SAE reporting purposes, AEs classified as 'unlikely' will be regarded as 'not related'; AEs classified as 'possible', 'probable/likely' and 'certain' will be regarded as 'related'.

### 6.3.3 Follow-up of unresolved AEs

Participants experiencing adverse events will be monitored with appropriate clinical evaluation and laboratory tests as indicated by the principal investigator. All subjects with adverse events will be followed until satisfactory recovery or stabilization are attained.

### 6.3.4 Reporting of adverse events

All Adverse Events must be recorded in the case report form, defining relationship to IMP and severity.

As soon as the Investigator is aware of a potential Serious Adverse Event (SAE), he/she should contact the local SMERUD monitor by phone, fax or e-mail, and in any case no later than 24 hours after the knowledge of such a case.

If identification of the event occurs outside of office hours, the emergency phone number described in the Investigator Site File may be used. At the time of the call, the Investigator must provide as a minimum requirement the participant enrolment number, birth date, nature of the SAE, and a preliminary assessment of causality. The Investigator should follow up the initial notification of the potential SAE by faxing a copy of the SAE reporting form to SMERUD at the number provided in the Investigator Site File. The faxed SAE reporting form should be received at SMERUD within 24 hours after knowledge of such a case.

#### **Smerud Medical Research International AS**

E-mail: [[contact]](mailto:[contact])

[contact]

[contact]

Follow-up information on an existing SAE that is fatal or life-threatening should be reported by the Investigator to SMERUD within 5 days after the initial report. Where appropriate, hospitalization or autopsy reports should be made available. All Serious Adverse Events will be followed up until resolution (i.e., asymptomatic, stabilization or death).

### 6.3.5 Reporting of suspected unexpected serious adverse reactions

Suspected unexpected serious adverse reactions (SUSARs) will be reported by SMERUD according to appropriate Competent Authority and Ethics Committee requirements. SMERUD will report SUSARs to Investigators on a regular basis according to ICH Good Clinical Practice and to local regulations. SUSAR reporting to the Competent Authorities and Ethics Committees will be performed according to local regulations in an unblinded manner. The Competent Authorities will be notified of all SUSARs through the Eudravigilance database.

Fatal and life-threatening SUSARs should be reported by SMERUD as soon as possible to the Competent Authorities and Ethics Committees according to local regulations, and in any case no later than seven calendar days, after knowledge by SMERUD of such a case. Relevant follow-up information on the case will be subsequently communicated within an additional eight days. All other SUSARs shall be reported to the Competent Authorities concerned and to the Ethics Committee concerned, according to local regulations, as soon as possible but within a maximum of fifteen days of first knowledge by SMERUD.

## 7 STATISTICAL METHODOLOGY AND DATA MANAGEMENT

The principal features of the statistical analyses to be performed are described in this section. A more technical and detailed elaboration of the principal features will be presented in a separate Statistical Analysis Plan (SAP), which will be signed and approved prior to database lock (DBL).

### 7.1 Estimation of Sample Size

So far, data from 375 children on IN sufentanil/ketamine show a safe and tolerable combination (data from PDC 01-0201, PDC 01-0203 and PDC 01-0206). Thus, from a safety perspective it is expected that 150 patients will be sufficient to capture and confirm the adverse event profile of the IMP. Furthermore, a sample size calculation was made for the primary efficacy endpoint on the basis of expecting a responder rate of 60%. A previous study reported a responder rate of 71.6 %, defined as pain intensity  $\leq 3$  at 30 min post IMP (16). With a sample of 113 patients, a one-sample one-sided proportion design would provide at least 80% power to show that the responder rate is more than to 60%, with a significance level of 5%. Accounting for an approximate 25% dropout rate the resulting sample size is 150.

### 7.2 Study Population

The analysis of data will be based on different subsets according to the purpose of analysis, i.e., for efficacy, safety/tolerability, respectively.

The decision regarding validity of data for each of the analysis sets will be made before DBL.

#### Enrolled population

The enrolled population consists of all enrolled participants regardless of receiving study treatment.

#### Full Analysis Set (FAS)

The full analysis set (FAS) will consist of all participants who received at least one dose of study treatment. The FAS follows the intention-to-treat (ITT) principle, i.e. participants will be analysed, regardless of whether treatment was received as planned. The FAS will be used for the analysis of primary and secondary objectives.

### 7.3 Method of imputation

The amount of missing data will be reported as appropriate, and no other imputation will be performed.

### 7.4 Method of statistical analyses

All data will be presented as descriptive analyses only. Continuous variables will be summarised using descriptive statistics (number of participants, mean, standard deviation [SD], minimum, median, maximum) by age group and as total. Categorical variables will be summarised in frequency tables (frequency and proportion) by age group and as total. Graphical presentations will be used as appropriate. All changes from baseline endpoints are calculated as the value of the corresponding timepoint minus the value at baseline.

Variables that are based on ordinal scales, such as pain intensity, will be summarized using median and interquartile range.

#### 7.4.1 Analyses addressing the primary objectives

##### **Primary safety and tolerability analysis**

For assessment of safety and tolerability, a multidimensional analysis using descriptive statistical methods will be conducted as follows:

##### **Adverse Events**

The number of subjects with adverse events, with possible treatment related adverse events, and with serious adverse events (SAE) will be summarised using counts and percentages of subjects by age groups. The number and percentage of subjects with adverse events by body system and preferred term will be summarised by age group. Adverse event severity and relationship to treatment will be summarised by body system, preferred term, and age group. Separate tables may be produced for SAEs depending on the number of SAEs occurring in the study. A 95% confidence interval will be computed for each percentage/proportion of adverse events.

##### **Respiratory Depression, Peripheral Oxygen Saturation, and Cardiovascular Stability**

These will be assessed by vital signs parameters of respiratory rate, peripheral oximetry, and pulse rate respectively. Measured values and changes from baseline will be summarised by mean, standard deviation (SD), 95% CI, median, minimum and maximum for each timepoint by age group and for all participants. Graphical representation of the measured values and changes from baseline in the form of boxplots will be produced for each timepoint (horizontal axis) by each age group and for all participants.

##### **Nasal irritation/Tolerability**

– The number of participants with nasal irritation will be summarised using counts and percentages of participant for each timepoint (30 and 60min post IMP administration) by age groups, dose level, and type of nasal irritation. A 95% CI of the percentage will be computed and reported.

## **Sedation**

the UMSS scores at assessment timepoints (baseline and 10, 15, 20, 30, 45, and 60 min after IMP administration) will be summarised using the median and IQR by age group and dose level. Graphical representations of UMSS scores in the form of boxplots will be produced for each assessment timepoint (horizontal axis) and for each age group. A 95% confidence interval of the mean UMSS score for each time point and by age group if appropriate (i.e., if data is normally distributed).

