Statistical Methods	
General principles The primary objective of this study is to investigate the safety, tolerability and analgesic effects of CT001 in pediatric participants when used in an acute care setting.
 
Data will be summarised using descriptive statistics. For continuous endpoints, the descriptive statistics include number of subjects, mean, median, standard deviation, standard error, lower and upper quartiles, minimum, and maximum. For categorical endpoints, frequency, and percentage will be given. Figures showing population distributions, such as box plots and histograms, will be reported for all applicable endpoints. The method of handling missing data for efficacy endpoints will be described for each set of endpoints. Missing data will not be imputed for safety endpoints.
 
Sample size estimation So far, data from 375 children on IN sufentanil/ketamine show a safe and tolerable combination (data from PDC 01-0201, PDC 01-0203 and PDC 01-0206). Thus, from a safety perspective it is expected that 150 patients will be sufficient to capture and confirm the adverse event profile of the IMP.
 
A formal sample size calculation was made for the primary efficacy endpoint on the basis of expecting a responder rate of 60%. A previous study reported a responder rate of 71.6 %, defined as pain intensity <math>\leq 3</math> at 30 min post IMP (16). With a sample of 113 patients, a one-sample one-sided proportion design would provide at least 80% power to show that the responder rate is more than to 60%, with a significance level of 5%. Accounting for an approximate 25% dropout rate the resulting sample size is 150.
 
Study populations The full analysis set (FAS) will consist of all patients who received at least one dose of study treatment (CT001). The FAS follows the intention-to-treat (ITT) principle, i.e. patients will be analysed regardless of whether treatment was received as planned. The FAS will be used for all analyses of primary and secondary safety and efficacy objectives.
 
The FAS will be used to tabulate demographic data, baseline disease characteristics, and subject disposition.
 
Statistical analysis of the primary endpoints The primary objective of the study will be evaluated using the FAS population. Data will further be evaluated by age group.
 
Descriptive statistics will be used for safety variables. Safety variables of special interest consist of vital signs, respiratory rate, pulse rate, oxygen saturation (SpO2), heart rate as well as sedation.
 
Clinically significant out-of-range values and clinically significant relevant changes of values will be described descriptive statistics, number of subjects, number of events.
 
Adverse events will be coded according to the MedDRA dictionary. The frequencies of adverse events will be tabulated by body system and "preferred term".

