#### 4.3.3 Assessment of sedation

The level of sedation will be assessed using the University of Michigan Sedation Score (UMSS, [Appendix D](#)). The UMSS has been validated for the assessment of procedural sedation in children. Level of sedation will be assessed at baseline (i.e. pre-IMP administration) and at 10, 15, 20, 30, 45, and 60 min post IMP immediately following each pain assessment. If a second dose of IMP is needed the sedation score will be performed at the same time points relative to the second dose.

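### Section 7.4.1 plans no count by UMSS level and no worst score per child for sedation, a primary safety variable; sections 6.2.1 and 4.3.3 time it from different doses after a second dose

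*Combined protocol and SAP*

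**What the plan says.** Section 6.2.1 lists UMSS sedation first among the primary safety and tolerability variables, and the Statistical Methods part of the Protocol Outline includes it among the safety variables of special interest. Appendix D defines five ordered levels, from 0 (awake) to 4 (cannot be roused).

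**Summary.** Under Sedation, section 7.4.1 states that the scores at baseline and at six post-dose timepoints "will be summarised using the median and IQR by age group and dose level". It adds boxplots by timepoint and age group. The only interval planned is "A 95% confidence interval of the mean UMSS score for each time point", and only if the data are normally distributed. This follows the general rule in section 7.4: "Variables that are based on ordinal scales, such as pain intensity, will be summarized using median and interquartile range". Elsewhere in section 7.4.1, adverse event percentages get 95% confidence intervals, and for nasal irritation "A 95% CI of the percentage will be computed and reported".

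The Protocol Outline has two general statements that could reach sedation: "Clinically significant out-of-range values and clinically significant relevant changes of values will be described descriptive statistics, number of subjects, number of events" and "Figures showing population distributions, such as box plots and histograms, will be reported for all applicable endpoints".

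**Timing after a second dose.** Section 6.2.1: "If a second IMP dose is needed, sedation will be performed at the timepoints relative to first IMP administration". Section 4.3.3: "If a second dose of IMP is needed the sedation score will be performed at the same time points relative to the second dose". Table 1 note a agrees with section 4.3.3. The Protocol Outline (Duration of Treatment) and section 4.2 (Part 2) continue safety assessments to 60 minutes after the last dose, or until rescue medication or procedures begin.

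**The concern.** The safety question for an opioid and ketamine combination is how many children became moderately or deeply sedated. A median and IQR on a five-level score that sits mostly at 0 does not answer it: any group making up less than about a quarter of the children can move up the scale without changing the tabulated values. Tables by timepoint also cannot show how many different children ever reached a given level.

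The timing conflict affects the children who receive two doses, who have the highest exposure in the study. If sites follow different sections, scores with the same nominal time will come from different times since the last dose. A site following section 6.2.1 would also stop scoring sooner after that dose.

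**Working it through.** The plan gives no sedation rate and no precision figure for sedation, so there is no stated figure to reproduce. From the document I use the target of 150 children (section 7.1), the minimum age-group sizes of 20 and 40 (section 5.4), the six post-dose timepoints (section 4.3.3) and the 10 to 15 minute gap between doses (section 5.3). All sedation counts below are assumed, for illustration.

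**1. Same median and IQR, different safety picture.** One timepoint, n = 150:

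| Dataset | UMSS 0 | 1 | 2 | 3 | Median (IQR) | UMSS ≥2 |
|---|---|---|---|---|---|---|
| A | 115 | 35 | 0 | 0 | 0 (0 to 0) | 0/150 = 0% |
| B | 115 | 20 | 12 | 3 | 0 (0 to 0) | (12 + 3)/150 = 10.0% |

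In both, 115/150 = 76.7% score 0, so the upper quartile is 0. This held under nine quartile definitions.

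Exact (Clopper-Pearson) 95% limits for k of n are the 2.5% quantile of Beta(k, n−k+1) and the 97.5% quantile of Beta(k+1, n−k). For k = 0 the upper limit is 1 − 0.025^(1/n).

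- A, UMSS ≥2: 0/150, 0 to 2.4%.
- B, UMSS ≥2: 15/150, 5.7% to 16.0%.
- B, UMSS ≥3: 3/150 = 2.0%, 0.4% to 5.7%.

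Neither dataset is near normal (Shapiro-Wilk W = 0.52 and 0.55, p < 1e-18 for both), so the conditional interval for the mean would not be produced. A boxplot would show the non-zero scores as outlying points, up to level 1 in A and level 3 in B, but with no percentage.

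**2. How much the table can hide.** With every other child at 0, up to 36 of 150, 9 of 40 or 4 of 20 children could be at UMSS 3 at a timepoint and the entry would still read 0 (0 to 0).

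**3. What an all-clear would mean in the smaller age groups.** With no child at UMSS ≥2, the exact upper limit is 1 − 0.025^(1/20) = 16.8% for 0/20 and 1 − 0.025^(1/40) = 8.8% for 0/40. An entry of 0 (0 to 0) conveys neither.

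**4. Per timepoint against per child.** Suppose 3 of 150 (2.0%) are at a given level at each of the six timepoints. If they are always the same children, 3/150 = 2.0% ever reached it. If they are all different, 6 × 3 = 18 and 18/150 = 12.0% (7.3% to 18.3%). The planned tables cannot tell these apart.

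**5. The two clocks.** On a first-dose clock, time since the second dose is the nominal time minus the gap:

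| Nominal time (min) | 10 | 15 | 20 | 30 | 45 | 60 |
|---|---|---|---|---|---|---|
| Gap 10 min | 0 | 5 | 10 | 20 | 35 | 50 |
| Gap 15 min | −5 | 0 | 5 | 15 | 30 | 45 |

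The 10-minute score thus falls 0 to 5 minutes before the second dose, and the last score 45 to 50 minutes after it. On a second-dose clock the last score falls 60 + 10 = 70 to 60 + 15 = 75 minutes after the first dose. Section 7.4.1 refers only to time after IMP administration, so the analysis does not settle which clock applies.

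**The case against.** The strongest reply is that much of this may be covered elsewhere. In the Protocol Outline the safety endpoints are adverse events, and UMSS appears only as an assessment. Sedation recorded as an adverse event would get a per-child percentage with a 95% interval. Section 7.4 provides frequency tables for categorical variables, and section 7.4.1 describes the pain scales as both ordinal and categorical, so counts by level are not clearly excluded. Histograms would show the spread across levels. Section 7 also presents itself as principal features only, with detail left to a separate SAP.

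These points narrow the finding but do not remove it. No rule links a UMSS level to an adverse event, and no level is defined as clinically significant. The sedation paragraph itself applies median and IQR. None of these routes yields a worst UMSS score per child or an interval for a UMSS proportion. The separate SAP is not in the document reviewed, so whether it closes the gap is unknown.

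Three further points stand. The counts are chosen, and 12% is the extreme of its range. The reference to dose level may already separate one dose from two, but the dosing text is redacted and this cannot be determined. The timing shortfall is at most 10 to 15 minutes, and monitoring may end earlier for rescue or procedures. Actual times of pain assessments are recorded and sedation is scored straight after pain, so most times can be reconstructed. A late score that was never taken cannot.

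**Conclusion.** Both parts hold. The timing conflict rests on no assumption: section 6.2.1 contradicts section 4.3.3 and Table 1 note a, the clocks differ by 10 to 15 minutes at every nominal timepoint, and section 7.4.1 names neither.

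The summary gap holds for the protocol text reviewed. Its size depends on assumed counts, because the document gives no sedation rates. In the illustration, a difference between 0% and 10.0% of children at UMSS 2 or above leaves the planned table unchanged. Boxplots or histograms would probably reveal that the two datasets differ, but without an interval or a per-child rate. No test or decision rule depends on sedation. The consequence is that a primary safety variable would be reported in a form that does not state how many children were sedated, or how deeply.

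**What to change.** In section 7.4.1 or the SAP, add for UMSS:

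- the number and percentage of children in each category at each timepoint;
- the worst post-dose score per child;
- the number and percentage of children at or above pre-stated levels (for example the Appendix D categories for moderate and deep sedation), with exact 95% confidence intervals, overall, by age group and by one versus two doses.

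Keep the median, IQR and boxplots as supplementary. State whether the Protocol Outline's counts of clinically significant values include UMSS, and from which level.

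Reconcile section 6.2.1 with section 4.3.3, Table 1 note a and section 7.4.1, and check the result against the Protocol Outline and sections 4.2, 4.3.2 and 6.1.1, so that sedation after a second dose has one stated time reference. Use actual assessment times for any child scored on the other clock.

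The cost is a few tables from scores already collected, specified before database lock, and one sentence on timing. A site clarification may be needed if any site followed section 6.2.1.
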